**Aim 2:**

Researchers may use AI to analyze de-identified data for Aim 2. This AI program may store data outside of UVA for future use.

**Primary Outcomes:** The rapid pilot tests in Aim 2 will assess changes from baseline to 6 weeks in knowledge about drinking and contraception, intention to change, self-efficacy for change, and readiness for change. The primary outcomes are differences in drinking and contraception behaviors from baseline to 6-weeks on the TLFB.

**Hypotheses:** The hypothesis is that some (and possibly all) of the piloted components will show effects on knowledge, intention to change, self-efficacy to change, and readiness to change. Additionally, we hypothesize that at least 2 of the piloted components will show significant change from baseline to 6 weeks on alcohol intake and contraception use.

**Analysis:** We will calculate baseline to 6-week improvements in knowledge about drinking and contraception, intention to change, self-efficacy for change, and readiness for change, and will calculate differences in drinking and contraception behaviors from baseline to 6-week on the TLFB. Intervention cost data (study budget, expense reports and labor costs) will be estimated using time-driven activity-based costing. We will calculate effect sizes of each component to identify those with the strongest effects on drinking and contraception for inclusion in the factorial experiment in Aim 3. The focus of this aim is to determine the effect size of each novel component, which is currently unknown. These findings will then inform the power for Aim 3.

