They will then be randomized to receive one novel component condition, each of which is designed as an engaging experience that boosts motivation to continue participating, for a 6-week period. All participants will complete the 4 Cores of the CARRII Native internet intervention over the 6-week period alongside the novel component.

The candidates that will be tested are: 1) Telephone-administered 30-day timeline follow-back (TLFB) of drinking, sex, and contraception, administered by phone, of alcohol intake and contraception type by sexual encounter at enrollment and monthly (2 weeks after enrollment), which should increase awareness of AEP risk and motivation for alcohol and contraception behavior change, 2) Mailed pregnancy tests sent monthly to raise consciousness of pregnancy risk and to detect a new pregnancy early, which should increase motivation for contraception behavior change, 3) Automated, personalized digital safer sex and drink counting/reduction skills training, to improve drinking self-management skills and self-efficacy for drinking reduction and contraception use, 4) Fully automated text messaging prompting usage of safer sex and drink reduction skills, to prompt behavior change, which should increase self-efficacy for behavior change, and 5) Access to an anonymized Community Message Board of Native women to discuss challenges in behavior change, to give and receive social support, which should increase perceived social support for behavior change.

We plan interim phone calls after 3 weeks in the pilot trial to check on progress.

Participants will complete a second TLFB for the past 6 weeks for drinking and contraception behavior, and a short survey to rate the component they experienced, along with the System Usability Scale on their component, and measures of short-term knowledge, intentions to change, self-efficacy for change, and readiness to change alcohol use and contraception behaviors.

This Aim will determine preliminary effect sizes on alcohol and contraception use and costs of each new component. New components with the highest effect sizes in the 6-week pilot trials will be integrated with the tailored CARRII core intervention.

**Is this study topic relevant to cancer risk factors, prevention, cancer treatment, or survivorship (e.g., pain, financial toxicity, etc.), or will the study purposefully include participants currently or previously diagnosed with cancer, or their caregivers?**

No

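### Aim 2 names no comparator for a component's effect size, and within-arm change mixes the component with the CARRII core that every arm receives

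*Combined protocol and SAP*

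**What the plan says.** The Aim 2 text in Data Reports & Storage defines the outcome as a change over time: "The primary outcomes are differences in drinking and contraception behaviors from baseline to 6-weeks on the TLFB". The behavioural hypothesis has the same form: "at least 2 of the piloted components will show significant change from baseline to 6 weeks on alcohol intake and contraception use". The Analysis paragraph then describes the target as something specific to each component: "The focus of this aim is to determine the effect size of each novel component, which is currently unknown". It adds: "These findings will then inform the power for Aim 3".

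The Study Overview says that the pilot should assess the independent effects of the components. It continues: "This Aim will determine preliminary effect sizes on alcohol and contraception use and costs of each new component", and "New components with the highest effect sizes in the 6-week pilot trials will be integrated with the tailored CARRII core intervention". Each woman is randomised to one of five components, and "All participants will complete the 4 Cores of the CARRII Native internet intervention over the 6-week period alongside the novel component". No core-only, waitlist or attention arm is listed. Every woman also completes a 30-day TLFB by telephone at baseline, and the same interview settles her eligibility. The follow-up TLFB covers six weeks.

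No section says what a component is to be compared with: the core alone, another component, or the average of the other arms.

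**The concern.** The quantity described (change within an arm) is not the quantity wanted (the effect of the component). The change within an arm is the sum of four parts: the core, the component, reactivity to being assessed, and any regression to the mean or time trend. Only the second belongs to the component.

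The documents make a shared shift plausible. The purpose section reports that CARRII significantly reduced the risk of alcohol-exposed pregnancy and pregnancy risk at 3 and 6 months, and drinking risk at 3 months, though in a nationwide sample and over a longer horizon. The TLFB is itself a candidate component, one "which should increase awareness of AEP risk and motivation for alcohol and contraception behavior change", and all arms receive it at enrolment. Because the eligibility interview is also the baseline, some regression to the mean is possible.

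Two things are at stake. An inert component could be reported as having worked. And if a pre-post effect size were entered into the Aim 3 calculation as the effect of a component switched on versus off, with the core in both, Aim 3 would be too small.

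**Working it through.** **No stated figure to reproduce.** The documents give no alpha, SD, allocation ratio, dropout or effect size for Aim 2. What follows is an illustration.

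**Inputs from the documents.** Maximum enrolment is 53, including up to 3 test users (Recruitment & Consent), with five components (Study Overview). With equal allocation this gives (53 − 3)/5 = 10 per arm.

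**Assumptions.** Two-sided 0.05, continuous outcomes, no dropout, independent arms, every component inert, and a shared standardised within-arm shift dz.

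**Step 1. One arm, one outcome.** The probability p of a significant improvement comes from the noncentral t with n − 1 = 9 df and noncentrality dz·√10. It is 0.134, 0.293 and 0.616 for dz 0.3, 0.5 and 0.8.

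**Step 2. One arm, both outcomes.** The hypothesis joins alcohol and contraception. If the outcomes are independent, the joint probability is p²: 0.018, 0.086 and 0.380. With correlation 0.5 (simulated) it is about 0.045, 0.143 and 0.447.

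**Step 3. At least 2 of 5 arms.** P = 1 − (1 − p)⁵ − 5p(1 − p)⁴, with p now the joint probability from step 2.

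| Shared shift (alcohol, contraception, in either order) | P(≥2 of 5 arms, both outcomes), correlation 0 to 0.5 |
|---|---|
| 0.3, 0.3 | 0.003–0.02 |
| 0.5, 0.3 | 0.01–0.05 |
| 0.5, 0.5 | 0.06–0.15 |
| 0.8, 0.3 | 0.06–0.11 |
| 0.8, 0.5 | 0.22–0.34 |
| 0.8, 0.8 | 0.63–0.74 |

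With 8 completers per arm, the equal-shift rows for 0.3, 0.5 and 0.8 become 0.002–0.01, 0.03–0.08 and 0.36–0.51. On a single outcome with 10 per arm the values are 0.14, 0.46 and 0.92, but that is a looser hypothesis than the one written.

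**Step 4. Regression to the mean.** If a fraction q of women is retained above a cut-off c at the baseline TLFB, and baseline and follow-up correlate at r, the expected shift is (1 − r)·φ(c)/q. For r = 0.6 and 0.7 this gives 0.46 and 0.35 SD at q = 0.3, 0.32 and 0.24 at q = 0.5, and 0.08 and 0.06 at q = 0.9. The values of q and r are assumptions.

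**Step 5. Aim 3, conditional illustration.** For a main effect with half the sample on and half off, N = 4(1.96 + 0.842)²/d². A true effect of 0.3 SD needs N = 349. If a pre-post value inflated to 0.4, 0.5 or 0.6 SD is used instead, N is 197, 126 or 88, and power at the true 0.3 SD, Φ(0.3√N/2 − 1.96), is 0.56, 0.39 or 0.29.

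**Step 6. Ranking.** Because arms are randomised and the core is common to all, it cancels in expectation from any difference between arms. What remains is noise. In simulation (10 per arm, r = 0.5, one outcome), two components truly 0.3 SD better than the other three come out as the top two with probability about 0.39 after baseline adjustment and 0.35 on raw change. At 0.5 SD the figures are 0.64 and 0.57. If all five are equal, the top arm still exceeds the mean of the others by 0.40 SD on average.

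**The case against.** The strongest reply is that little depends on this. Within Aim 2 the effect sizes are used to choose components, and that choice is a ranking. The plan calls the effect sizes preliminary, weighs cost and practicality too, and attaches no go/no-go rule to the hypothesis. All of this stands, and it limits the severity.

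Three stronger readings are tempting, and the documents do not support them.

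- *The core will lead the trial to pick the wrong components.* A shift common to randomised arms does not systematically favour any of them. The ranking is noisy at about 10 per arm, which is a separate matter.
- *Inert components will probably satisfy the hypothesis.* On both outcomes this needs a shift of about 0.8 on each. The documents give no magnitude for the core, and the purpose section's report of a longer-lasting effect on pregnancy risk than on drinking risk gives reason to doubt equal shifts.
- *Aim 3 will be underpowered.* The documents contain no Aim 3 calculation and say only that the pilot findings will inform it. The loss in step 5 follows only if pre-post values are entered as on-versus-off effects.

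The upper end of the regression-to-the-mean range is also weak. The interest form pre-screens on drinking and contraception before the baseline interview, so the TLFB should reject fewer women and some regression may already have happened. The 0.46 SD figure is the least plausible end.

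One could also argue that effect size was always meant as a between-arm contrast. The Aim 2 text does not say so, and the behavioural and attitudinal quantities it describes are baseline-to-6-week changes.

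**Conclusion.** The point holds in limited form. As written, Aim 2 measures each component by within-arm change and calls the result that component's effect size. With the four Cores and the enrolment TLFB in every arm and no core-only arm, that change is not the independent effect the Study Overview asks for. Significant change in an arm is not evidence that its component works, whatever the probability of a false success.

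The size depends on a shared shift that the documents do not give. Under the stated assumptions, false success on both outcomes is unlikely for shifts up to 0.5 (at most 0.15) and likely only for a large shift on both (0.63–0.74 at 0.8 and 0.8). The harm is to interpretation and, conditionally, to Aim 3 power. It lies between a minor point and one that should be fixed.

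**What to change.** Make these changes as a documented amendment before outcome data are analysed. The Unexpected Adverse Events section shows that Aim 2 is already under way.

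1. Express each TLFB outcome per day or as a proportion, so that the 30-day baseline and 6-week follow-up windows are comparable. Fit one model of the 6-week value on baseline plus arm, in a form suited to the outcome; contraception is recorded by sexual encounter and may not be continuous. Report missing follow-up by arm. Give each arm's adjusted value against the average of the other four with a 95% CI, for ranking only. This contrast is 5/4 of the arm's deviation from the grand mean, so it orders arms exactly as the adjusted means do. The gain in ranking comes from the baseline adjustment.
2. Keep pre-post change as descriptive, label it core plus component, and state that significant within-arm change is not evidence of component efficacy. Do not turn the hypothesis into a between-arm significance test. The contrasts sum to zero across arms, and in simulation at least 2 arms would be significantly better with probability 0.0015 if all five components are worth 0.5 SD, and 0.034 if only two are.
3. State that benefit over the core alone is not identified in Aim 2, and that the TLFB arm's contrast reflects only its additional TLFB, because all arms receive the one at enrolment.
4. State that pre-post changes will not be used as the Aim 3 on-versus-off effect. The pilot may inform the SD and the baseline–follow-up correlation, with the Aim 3 effect justified separately.

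Cost: no new participants or data. The contrasts are relative and imprecise. Their standard error is √(1 − r²)·√(1/n + 1/(4n)) SD, which at r = 0.5 is 0.306 for 10 per arm and 0.342 for 8, giving 95% half-widths of about 0.6 and 0.7 SD. The pilot would also no longer supply an effect size for Aim 3.

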Mixed methods research during Aim 1 will include 4 different components. They are: 1. Convene working group of Native American stakeholders. This will include indigenous women from the Southwestern region, urban Denver and the Mountain West region, where consultant [name] is located and conducts Native health studies, and the Great Plains regions of Minnesota, South Dakota, and North Dakota where University of Minnesota-Duluth partner researcher [name] is located and routinely recruits for her research. Indigenous women from the Mid-Atlantic may also be recruited, as UVA's indigenous representative, [name], is connected to several tribes and groups of Native Americans residing in this region.

2. Collect data using a 35-minute survey of demographics, AEP risk, device use, recommendations for recruitment methods, and interest in subsequent trial with 300 Native women respondents, targeting approximately 100-150 per region (rural Great Northern Plains), urban Denver and rural mountain West and Southwest.

3. Conduct Iterative prototyping of existing and proposed CARRII components with 60 Native women across 10 Focus Group discussions. Content will be informed by Components 1 and 2.

4. Conduct User Testing of existing CARRII and candidate components with Think-Aloud methods among 20 Native women.

In Aim 2, we will Pilot test 5 new candidate components tailored to Native women at risk of AEP: After incorporating input from participants (SA 1) and the Native Partners Working Group, we will pilot candidate components to assess independent effects on AEP behavioral risk factors (drinking and contraception) while considering practical aspects such as frequency and duration of contact with participants, and costs of each component.

Participants will be Native women aged 18-44 with some drinking and some risk for pregnancy (some ineffective contraception use). Participants must have access to the Internet via a device they can access at least weekly. Each participant will complete a baseline survey including a telephone-administered 30-day Timeline follow-back of alcohol use and contraception use, to determine eligibility, and a short online survey evaluating knowledge about AEP risk, intentions and self-efficacy to change, and readiness to change alcohol and/or contraception behaviors.

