Women who have participated in the Survey component of Aim 1 are also eligible to participate in either or both of these components.

We are focusing our recruitment efforts on tribal communities in the Rocky Mountains, Great Plains, and Great Lakes, and urban centers with large pockets of Natives, as well as those that are near tribal communities (e.g., Minneapolis, MN; Rapid City, SD; Denver, CO). We will utilize methods proven for recruitment by partners including: 1) posting flyers at local gathering places and community events, 2) radio/print advertisements in local and regional outlets, 3) posting and paid advertisements on social media, 4) attending local events (e.g., health fairs, powwows) to administer surveys, and 5) working with community partners to provide information to patrons and refer participants to the study. Participants who express interest in the study will be provided information and, if interested, verbal consent will be obtained.

Community partner Missouri Breaks Industries Research Inc. (Missouri Breaks) will recruit participants for both the Focus Groups and Think-Alouds.

Aim 2 Recruitment: 53 Native women and others who can become pregnant, ages 18-44 years of age, considered near-eligible, with some drinking and some risk for pregnancy (some ineffective contraception use), and access to the Internet via a device they can access at least weekly (including up to 3 test users who are also near-eligible). Same as the above methods. Each of these methods will result in a potential participant completing a study interest form in Qualtrics. Study coordinator will utilize TransUnion's TLO Identity Check to verify they are a real person, are 18-44 years old, and female. Coordinator will send email to interested participants, to schedule the consenting process and Baseline phone call. The email will contain the study Drink card and Contraception card, in order to facilitate the 30-day TimeLine Follow-Back, which will determine eligibility.

Women who have participated in the Survey component of Aim 1, or the Think-Aloud or Focus Group Discussion, are also eligible to participate in Aim 2 if they meet the additional criteria. Past participants of any of those components who indicated interest in future participation may be contacted by the coordinator for recruitment to Aim 2. Participants in Aim 2 are also eligible to complete the Survey component.

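### Choosing components for Aim 3 on unadjusted change from baseline, with about 10 women per arm, tends to favour the arm that starts worse by chance; a baseline covariate removes this at no data cost, for a modest gain in ranking

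*Combined protocol and SAP*

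**What the plan says.** Under Data Reports & Storage, Aim 2, the plan states: "The primary outcomes are differences in drinking and contraception behaviors from baseline to 6-weeks on the TLFB". The analysis sentence repeats this: the team "will calculate differences in drinking and contraception behaviors from baseline to 6-week on the TLFB". The use of the result follows: "We will calculate effect sizes of each component to identify those with the strongest effects on drinking and contraception". The same paragraph says that the findings will inform the power of Aim 3. The Study Overview gives the same selection rule, the highest effect sizes going forward.

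On design, the Study Overview says "we will Pilot test 5 new candidate components tailored to Native women at risk of AEP" and "They will then be randomized to receive one novel component condition". It adds: "All participants will complete the 4 Cores of the CARRII Native internet intervention over the 6-week period alongside the novel component". Recruitment & Consent gives the size: "Aim 2 Recruitment: 53 Native women and others who can become pregnant", "including up to 3 test users who are also near-eligible".

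No model, covariate, effect-size formula, standardising SD, allocation ratio, alpha or power is given for Aim 2.

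**The concern.** The effect sizes are used to choose between arms. A change score subtracts the whole baseline value, whereas the follow-up value carries only a fraction r of a baseline deviation, where r is the baseline/follow-up correlation. An arm that starts one SD worse by chance therefore shows an extra (1 − r) SD of apparent improvement with no component effect. Randomization balances baselines on average over repeated trials, but this pilot is run once with arms of about 10, and chance gaps at that size are not small.

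Two things are at stake: which components are carried to Aim 3, and the precision of the effect sizes that feed its power calculation. The baseline values needed to adjust are collected from every participant anyway.

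**Working it through.** The plan has no sample-size or power figure for Aim 2, so there is none to reproduce.

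**Inputs from the documents.** Five arms; 53 enrolled, up to 3 of them test users. Per arm: (53 − 3)/5 = 10, or 53/5 = 10.6 if all are randomized.

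**Assumptions, not in the documents.** Equal allocation, no dropout, normal data, equal SD at baseline and follow-up (set to 1), and r = 0.3, 0.5 or 0.7.

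**Formulas, with n = 10 per arm.**
- Expected gap between the highest and lowest of five baseline arm means: 2.326/√10 = 0.74 SD.
- Part of that gap that change scores pass on as apparent effect: (1 − r) × 0.735 = 0.51, 0.37, 0.22 SD.
- Correlation of an arm's baseline mean with its mean reduction: √((1 − r)/2) = 0.59, 0.50, 0.39.
- Variance per woman: change score 2(1 − r) = 1.40, 1.00, 0.60; baseline-adjusted 1 − r² = 0.91, 0.75, 0.51. The ratio is (1 + r)/2 = 0.65, 0.75, 0.85.
- SE of a two-arm contrast, √(2 × variance/10): change score 0.53, 0.45, 0.35; adjusted with known slope 0.43, 0.39, 0.32.

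**Simulation** (5 arms of 10, common slope estimated from the data; change score → adjusted):

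| Quantity | r = 0.3 | r = 0.5 | r = 0.7 |
|---|---|---|---|
| Contrast SE (SD) | 0.53 → 0.43 | 0.45 → 0.39 | 0.35 → 0.32 |
| Contrast variance ratio | 0.67 | 0.77 | 0.87 |
| No true differences: worst-starting arm ranks first | 46% → 20% | 41% → 20% | 35% → 20% |
| No true differences: total best-to-worst gap (SD) | 0.87 → 0.71 | 0.74 → 0.64 | 0.57 → 0.53 |
| True effects 0, 0.1, 0.2, 0.3, 0.4 SD: best ranked first | 37% → 41% | 40% → 43% | 46% → 47% |
| Same effects: best in top two | 62% → 66% | 66% → 69% | 72% → 74% |

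Before rounding, the rank-first gains are 3.8, 3.0 and 1.8 points. The variance ratios are 0.02 above theory, which is the price of estimating the slope. In precision, 50 women analysed with adjustment are worth 50/0.67 = 75, 50/0.77 = 65 or 50/0.87 = 57 analysed by change score. Error degrees of freedom fall from 50 − 5 = 45 to 44.

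**Direction.** For drinking, where lower is better, the arm starting highest gains. For effective contraception use, knowledge, self-efficacy and readiness, where higher is better, the arm starting lowest gains.

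**Choice of standardiser.** The residual SD of the adjusted model is √(1 − r²) of the raw SD. Dividing by it inflates effect sizes by 1/√(1 − r²) = 1.05, 1.15 or 1.40. Carried into an unadjusted Aim 3 power calculation, those values would overstate power.

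**The case against.** The strongest reply is that the benefit is small where it counts. Even with equally effective components, adjustment shrinks the total chance gap between best and worst arm by only 0.16, 0.09 or 0.04 SD (0.87 − 0.71, 0.74 − 0.64 and 0.57 − 0.53, from unrounded values). A reader might infer from the 0.51, 0.37 or 0.22 SD figures that this much would disappear from the ranking. It would not: those figures are only the baseline-driven part of the noise, and the spread from having 10 women per arm survives. This objection stands and limits the size of the point.

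A reader might also infer that the plan commits to raw change scores, or standardises by each arm's own SD. The documents support neither. They name differences and effect sizes without a formula; unadjusted change is the plain reading, but adjustment is not ruled out. Nor does the highest-starting arm always gain: this is a tendency, and its direction depends on the outcome.

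That Aim 2 is only a pilot does not dispose of the point. Its stated product is a set of effect sizes used to select components and inform Aim 3 power.

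**Conclusion.** The point holds in limited form. The only stated basis for selecting components is unadjusted change, and at about 10 per arm this ties the ranking partly to chance baseline levels: the worst-starting arm ranks first 46/41/35% of the time, against 20% by chance, when nothing differs. Adjustment removes that dependence and lowers contrast SEs by roughly 7% to 19% (0.346 to 0.323 at r = 0.7; 0.529 to 0.431 at r = 0.3). Correct selection improves by only about 2 to 4 points.

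The figures rest on the assumed r, equal allocation, no dropout and normal data. The gain shrinks as r nears 1, and drinking data are likely to be skewed, so all figures are approximate.

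It would go too far to conclude that adjustment makes the pilot's ranking reliable. It also would not rescue the hypothesis of significant change within components. Regression to the mean is shared by all arms, since the baseline TLFB also decides eligibility. The effect of the Cores is likewise shared, and no Cores-only arm exists. Adjustment repairs comparisons between arms and nothing else.

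**What to change.** In the Aim 2 analysis paragraph, before arms are compared:

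1. Keep the within-component change from baseline as a descriptive summary for the stated hypothesis.
2. For ranking, add one model per outcome across all five arms: 6-week value on component arm, with the baseline value of the same outcome as covariate. Do this for the drinking and contraception outcomes and for knowledge, intention, self-efficacy and readiness.
3. Express TLFB outcomes as per-day rates or proportions. The baseline window is 30 days and the follow-up window 6 weeks, and the Unexpected Adverse Events section adds 16 days to the study period, so totals are not comparable.
4. Rank on the baseline-adjusted contrast of each arm with the mean of all arms. Standardise by the pooled baseline (raw) SD, not the residual SD, so that the values can be carried to Aim 3 without inflation.
5. State that these contrasts compare components with each other and not with the Cores alone.

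The cost is wording and one error degree of freedom. No new data are needed.
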